### **9.2.2 *Removal from Investigational Product***

Removal from investigational product administration concerns subjects who do not receive a complete study vaccination schedule as planned per protocol. A subject who is withdrawn from further study vaccine administration need not necessarily be withdrawn from the study as further study procedures or follow-up may be performed (safety or immunogenicity) if planned in the study protocol.

Information pertaining to premature discontinuation of the study vaccine will be documented in the eCRF. The Investigator will document whether the decision to discontinue further vaccination was made by the subjects' parent(s)/guardian(s) or the Investigator, and which of the following possible reasons was responsible for withdrawal:

- SAE/IME.
- AE.
- Other (specify).

## **10. STATISTICAL METHODS**

### **10.1 STATISTICAL ANALYSIS**

All statistical analyses will be performed by Assign Data Management and Biostatistics GmbH, [name] using SAS® software (SAS Institute Inc., Cary, NC, USA) under the supervision and responsibility of the Sponsor.

All statistical methods shall be detailed in a Statistical Analysis Plan (SAP) that will be finalized before database lock.

Data **obtained in Stage II from candidates 1 and 2 (2018 lots)** from this study will be combined with data from the historical control study (M2) to enable assessments and comparisons described in the study objectives. In general, data from this study will be presented alongside these historical components, as if the data were collected simultaneously.

Unless otherwise specified, descriptive statistics include mean, standard deviation (SD), median, maximum, minimum, and range for continuous variables and the number and percentage in each group for categorical variables.

Unless specified otherwise in the SAP, statistical tests and confidence intervals (CIs) will be computed using a two-sided 5% significance level. Exact (Clopper-Pearson) CIs will be used for univariate summaries of dichotomous variables, and Miettinen-Nurminen score-based confidence intervals will be used for rate differences.

**Data obtained in Stage I from candidate 2 (2016) from this study will be analyzed descriptively, and summarized in an interim report.**

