### Statistical Methods:

#### Sample size

As in the historical control comparator study M2, this study has safety and Day 28 post-initial vaccination seroprotection rate as primary endpoints. Each age group will be monitored for safety; the primary immunogenicity endpoint, however will be limited to the infant groups **administered 2018 lots of vaccine candidates**, to which both 1- and 2-dose groups will contribute. The primary comparisons will entail comparisons of post-first-dose data from the four infant groups administered 10^5 and 10^6 dose levels of candidate 1 [2018] and candidate 2 [2018], to the corresponding infant cohort from study M2. **Data obtained for candidate 2 2016 material will be summarized, and not involved in direct comparisons with the historical control.**

The sample size for the older children (Groups A1H2[2018], A2H2[2016], and A2H2[2018]) is chosen to provide adequate safety data prior to age de-escalation. Forty-five subjects are required to have 90% probability of observing at least one occurrence of an adverse event, when the true adverse event rate is 5%. Allowing for a 10% non-evaluability/dropout rate requires 50 subjects for the safety evaluations. Immunogenicity will be assessed as a secondary endpoint in the older cohort.

For the primary immunogenicity endpoint, it is assumed that the seroprotection rate following administration of a single dose of Sabin mOPV2 and **2018 lots of candidate nOPV2 vaccines** in this population will be  $\geq 95\%$ . In the historical control comparator study, M2, a total of 91 per-protocol subjects (a 20% dropout rate from the enrolled population) were available for the immunogenicity endpoint in the younger cohort. For the current study, 129 evaluable (per-protocol) subjects per vaccine candidate and per dose level are required such that 90% power is available to declare non-inferiority to the Sabin 2 control, using the lower confidence bound of the Miettinen-Nurminen score confidence interval for inference (one-sided alpha = 0.025 for each candidate vaccine and dose level, separately, non-inferiority margin 10%). Therefore, assuming a 20% dropout rate the required enrollment is 162 subjects. Since the safety endpoint requires 50 subjects, and all subjects contribute to the immunogenicity endpoint, 50 randomly-chosen subjects will be assigned to receive two doses, and the remaining 112 subjects will receive only a single dose of each candidate vaccine.

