## **Immunogenicity**

### ***Neutralizing Type 2 Poliovirus Antibody Titers***

At each pre-and post-vaccination time point where neutralizing antibody titers are obtained:

- Seroprotection rates with 95% confidence intervals (CIs) will be computed.
- Seroconversion rates with 95% confidence intervals (CIs) will be computed at post-vaccination time points. Seroconversion will be computed from Day 0 for all subjects, and additionally from Day -84 for infant subjects.
- Median of log2 and geometric mean antibody titers (GMT) will be computed along with 95% CIs.
- Plots of the reverse cumulative distribution of antibody titers will be generated for each group.

The primary immunogenicity endpoint, seroprotection 28 days after a single dose in **each 2018 candidate nOPV2** infant group, will be compared with the corresponding group receiving Sabin mOPV2 from the historical control study (M2) by computing the two-sided 95% Miettinen-Nurminen score confidence interval for the difference in seroprotection rates (nOPV2 candidate minus control), and comparing the lower bound of this interval with the non-inferiority margin, -10%, in order to establish non-inferiority. In order to control one-sided type I error at level  $\alpha = 0.05$  overall, each candidate will be compared with the control at one-sided level  $\alpha^* = \alpha / 2 = 0.025$ . In addition, the high dose level of each **2018** candidate will be compared with the control, and only if the non-inferiority endpoint is met, the low dose level will also be tested with the same test-level type I error rate. This fixed-sequence enables control of multiplicity within each candidate-level type I error rate for the multiple dose level comparisons.

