**Further investigation is underway in adults** (study M4) from whom additional safety and immunogenicity data will be obtained. Although the long-term collection of safety data will still be ongoing at the time of enrolment for the present study in young children and infants, this study was only initiated when adequate safety follow-up of the M4 study in adults had been obtained according to the sponsor and DSMB. The present study is being performed to generate data in a similar fashion on the safety, immunogenicity (humoral and intestinal) and genetic stability endpoints of these novel nOPV2 candidates in children aged 1 to 5 years and in infants approximately 18 weeks of age vaccinated with bOPV-IPV. The overall development of nOPV2 was designed before the global cessation of OPV2 use which allowed studies to be started with mOPV2 before April 2016 with similar study design to this one (specifically M2) to provide historical control data against which to compare the novel nOPV2 candidates. This will allow comparison of data from this study with data that is already being generated on the immunogenicity, safety, and genetic stability of the mOPV2 vaccine in M2 in a comparable 18–22 week-old infant population (prevaccinated with bOPV and IPV). These comparisons will support the selection of which candidate to take further in development.

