#### Immunogenicity:

- Median and geometric mean antibody titers of type 2 polio neutralizing antibodies at Day 0 and at 28 days after the first dose of nOPV2 in all groups, and 28 days after the second dose of nOPV2 in **all groups receiving two doses**.
- Seroconversion rate at Day 28, 28 days after the first dose of nOPV2 in all groups, and **at Day 56**, 28 days after the second dose of nOPV2 in all groups receiving two doses. Seroconversion is defined as a change from seronegative to seropositive, or in seropositive subjects as an antibody titer increase of  $\geq 4$  fold over Day 0 titer corrected for maternal antibody titers where applicable/age-appropriate.
- Seroprotection rate of type 2 polio neutralizing antibodies at Day 0 in all groups, at 28 days after the first dose of nOPV2 **in all 1 to 5 year-old groups, and at Day 56**, 28 days after the second dose of nOPV2 in **all 1 to 5 year-old groups and two-dose infant groups**.

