### 3.3 EXPLORATORY ENDPOINTS:

- Median and geometric mean antibody titers of type 2 polio neutralizing antibodies in infants at 6 weeks of age (Day -84) before receiving their first bOPV vaccination to provide a measure of maternal antibodies.
- Descriptive and exploratory analysis of 1 to 5 year-olds and 18–22 week-old infants developing a polio type 2 seroconversion within 1 week of nOPV2 exposure, i.e. 7 days after their first dose of nOPV2.
- Descriptive analysis of viral shedding **following a second dose** in 1 to 5 year-olds, and infant groups administered **two 10^6 CCID50 doses** of each nOPV2 candidate.
- **Descriptive analysis of viral shedding in all infant groups administered one 10^5 CCID50 dose of each nOPV2 candidate.**

- Descriptive analysis of viral shedding in all infant groups administered two  $10^5$  CCID50 doses of each nOPV2 candidate.
- Exploratory endpoints may also include assessment of the genetic stability of shed virus at one or more time points following two doses  $10^6$  CCID50 of each nOPV2 candidate, following one dose of candidate 2 (2016), or one or two  $10^5$  CCID50 doses of all nOPV2 candidates.
- Exploratory endpoints may also include assessment of the potential for neurovirulence of shed virus at one or more time points following two  $10^6$  CCID50 doses of nOPV2 candidates, following one dose of candidate 2 (2016), or one or two  $10^5$  CCID50 doses of nOPV2 candidates.
- Assessment of antibody levels and proportions displaying protective levels against HBV antigen ( $\geq 10$  mIU/mL) and PRP antigen ( $\geq 0.15$   $\mu$ g/mL) in all infant groups 4 weeks after the last dose of DTPw-HBV-Hib (coincides with Day 0 serum sample for polio antibodies).

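### The primary non-inferiority test against the historical M2 infants makes no adjustment for Day 0 type 2 immunity, so a Day 0 gap between the studies biases the verdict in a direction nobody can know in advance

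*Combined protocol and SAP*

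**What the plan says.** The primary immunogenicity endpoint is the share of infants with a type 2 titre of at least 1:8 at Day 28 (3.1). The Synopsis compares each 2018-lot infant group with M2 "by computing the two-sided 95% Miettinen-Nurminen score confidence interval for the difference in seroprotection rates", and decides by "comparing the lower bound of this interval with the non-inferiority margin, -10%, in order to establish non-inferiority". Section 10.2 adds one-sided alpha 0.025 per candidate with the high dose tested first, 129 evaluable infants per group, 91 per-protocol M2 controls and an assumed rate of at least 95% in both. No covariate, stratum, matching or rule for a baseline imbalance is given.

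The control is not concurrent. Section 1.2 explains that the programme's timing "allowed studies to be started with mOPV2 before April 2016 with similar study design", naming M2, and calls the M2 infants comparable. Amendment 2, which sets up the present Stage II, is dated March 2019. Section 4.2 randomises Stage II infants to candidate and number of doses only. Section 10.1 pools the two studies for the planned comparisons and shows them together: "data from this study will be presented alongside these historical components, as if the data were collected simultaneously".

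Baseline titres are collected. Section 3.2 lists "Seroprotection rate of type 2 polio neutralizing antibodies at Day 0 in all groups" as a secondary endpoint, and 3.3 has a Day −84 titre "before receiving their first bOPV vaccination to provide a measure of maternal antibodies". Seroconversion is computed from Day 0 (8.2.1) and contrasted with M2 (2.2), so Day 0 titres should exist in both studies.

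**The concern.** The endpoint asks only whether the Day 28 titre reaches 1:8. Every infant has had IPV about four weeks before Day 0, and some may still carry maternal antibody. Part of each cohort may therefore already be at or above 1:8 when nOPV2 or mOPV2 is given, and those infants can count as successes whatever the vaccine does. If that part differs between M5 and M2, the crude difference mixes a vaccine effect with a baseline effect.

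Higher Day 0 protection in M5 makes a weaker candidate look acceptable. Lower protection makes an equal candidate fail. The result feeds candidate and dose selection (1.2, 10.1.2), and the high-dose result also decides whether the low dose is tested at all (10.2).

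**Working it through.** **Inputs from the documents (Synopsis, 10.2).** 129 nOPV2 and 91 M2 infants; 95% in both arms; margin −10 points; one-sided alpha 0.025; Miettinen-Nurminen score test.

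**The plan's own figure.** Exact binomial enumeration of that test gives power 0.904 at 95% vs 95%. Enrolment is 129/0.8 = 161.25, so 162. Both agree with 10.2. At 85% vs 95% the false non-inferiority rate is 0.0215. The sample size is sound; the issue is bias.

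**Model (assumption).** Let b be Day 0 seroprotection and s the response among Day 0 seronegatives. Infants protected at Day 0 are taken to stay protected. Then

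Day 28 rate = b + (1 − b) × s

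and the bias in the tested difference = (b_M5 − b_M2) × (1 − s), with s the candidate's response.

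**Assumed range.** The documents give no Day 0 rate for either study, so b_M2 is set at 30%, 50% and 70%, with M2 at 95% on Day 28. For b_M2 = 50%:

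- Equal vaccine: s = (0.95 − 0.50)/0.50 = 0.90.
- Candidate exactly 10 points worse in an M2-like cohort: s = (0.85 − 0.50)/0.50 = 0.70.
- With M5 at 60% on Day 0, the second candidate reaches 0.60 + 0.40 × 0.70 = 0.88. The tested difference is −7 points instead of −10, and the bias is 0.10 × 0.30 = 3 points.

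**Results (exact enumeration).**

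| | b_M2 30% | b_M2 50% | b_M2 70% |
|---|---|---|---|
| False non-inferiority, no gap | 0.021 | 0.021 | 0.021 |
| M5 5 points higher | 0.039 | 0.050 | 0.084 |
| M5 10 points higher | 0.070 | 0.107 | 0.259 |
| Gap at which it reaches 0.05 | about 7 points | about 5 points | about 3 points |
| Power, equal vaccine, no gap | 0.904 | 0.904 | 0.904 |
| Power, M5 10 points lower | 0.833 | 0.799 | 0.710 |

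Per 10-point Day 0 gap, the bias is 0.7 to 1.7 points for an equal vaccine and 2.1 to 5.0 points for one at the margin.

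**Which weights remove it.** With response 70% vs 90% among seronegatives, the adjusted difference is −20 points × the seronegative share used as weight.

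- M2 weights (50% seronegative): −20 × 0.50 = −10, whatever the M5 baseline.
- nOPV2-group weights: −20 × 0.40 = −8 when M5 is 60% protected at Day 0, and −20 × 0.30 = −6 at 70%.

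Simulation agrees. At 60% vs 50%, false non-inferiority is about 0.03 with M2 weights and about 0.11 with nOPV2 weights, against 0.107 crude. At 70% vs 50%, nOPV2 weights leave about 0.36, against 0.375 crude.

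**The case against.** - **The size is assumed.** This stands. No Day 0 rate is given, and nothing shows that a gap exists or which way it would run. Section 1.2 describes similar design, age and priming, which makes a large gap less likely but does not exclude one.
- **A reader might infer that a Day 0 gap passes one-for-one into the verdict.** It does not. It is multiplied by (1 − response among seronegatives), and so is small if nearly all seronegatives respond. It matters most near the margin.
- **A reader might infer that the study ignores baseline.** It does not. Day 0 seroprotection, titres and seroconversion are secondary endpoints, and 10.1.2 promises formal comparison of primary and secondary immunogenicity endpoints with M2. An imbalance could be seen, but it could not change the primary verdict.
- **A reader might take the presentation sentence in 10.1 as the fault.** Deleting it would alter no test. The unadjusted rule is in the Synopsis and 10.2.
- **A reader might say the 10-point margin is diluted because only seronegatives can respond.** The protocol chose seroprotection in all infants as its endpoint. A margin among seronegatives is a different estimand, not a correction.
- **"False" depends on the reference cohort.** This stands. In an M5 cohort 70% protected at Day 0, the illustrative candidate is 0.30 × 20 = 6 points worse, inside the margin. It is at the margin only by reference to the M2 baseline.
- **Detail is left to a SAP.** Section 10.1 says so, and no separate SAP text is available here. An adjusted analysis may yet appear there, but the protocol neither contains nor requires one.

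**Conclusion.** The point holds as a weakness in the confirmatory analysis that should be fixed. It is not a sample-size error and not evidence that the two cohorts differ. The verdict rests on a crude comparison with a non-randomised, earlier cohort, and it leaves out a baseline measurement that the trial already takes and that bears directly on the endpoint.

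Under the assumed range, a 10-point Day 0 gap raises false non-inferiority from 2.1% to about 7–26%, or lowers power from 90% to about 71–83%, depending on its direction. These figures assume that infants protected at Day 0 remain so, that M2 is at 95% on Day 28, and that the margin is read in the M2 population. Adjusting for Day 0 serostatus addresses this source of bias only. Other differences between the studies would remain.

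**What to change.** In 10.1.4 and the SAP, before Stage II results are unblinded, pre-specify a Day 28 seroprotection difference adjusted for Day 0 serostatus (<1:8, ≥1:8). Section 10.1.2 makes the formal M2 comparisons at the Stage II database freeze, so the rule must be settled before that freeze, not merely before final lock.

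- Use a stratified Miettinen-Nurminen interval or a standardised risk difference, standardised to the M2 Day 0 distribution, so that the 10-point margin keeps its meaning in the control population.
- Do not use nOPV2-group weights for this purpose. They leave most of the false non-inferiority in place.
- Let the interval reflect uncertainty in the weights. A simple version that treats the M2 share as known was somewhat liberal: 0.027 to 0.054 with no gap, and up to 0.066 across the range examined.
- Report the adjusted interval together with the crude interval and the Day 0 seronegative stratum.
- State that non-inferiority is not claimed on the crude interval alone if the adjusted interval fails.

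The cost is protocol and SAP wording and one further analysis, with no new sampling. Infants without a Day 0 titre drop out. Power for an equal vaccine is lower when M5 has the higher Day 0 protection (about 0.865 against 0.967 crude at 60% vs 50%). It is higher when M5 has the lower (about 0.95 against 0.80 at 40% vs 50%), although these adjusted figures come from the simple, slightly liberal version.

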#### **10.1.1 Study Populations**

The following populations will be considered for analysis:

- Total Vaccinated population, defined as all subjects who received at least one dose of study vaccine.
- Per-Protocol (PP) population, consisting of all eligible study participants who are in the Total Vaccinated population and who receive all of the immunizations scheduled for the group to which they are allocated and excludes those subjects who received any therapy that could significantly affect the subject's immune status and those subjects who meet criteria outlined in Section 5.3. The per-protocol population will be adapted by time point to allow subjects to contribute data to per-protocol analyses until such time as they become disqualified. All deviations and violations occurring in the study will be reviewed prior to database lock and classified as either minor or major.

Unless specified otherwise, the Total Vaccinated population will be used for safety/tolerability analysis and analysis of demographics. Immunogenicity and viral shedding analyses will be primarily conducted in the per-protocol population.

### 10.1.2 *Analysis Sequence*

An interim analysis of safety, immunogenicity, and viral shedding will be conducted following completion of a minimum of 28 days of safety follow-up following each dose in 1 to 5 year-old and infant groups administered candidate 2 (2016) in Stage I.

In order to enable data review and candidate/dose selection decisions which may impact future clinical development plans prior to completion of the extended safety follow-up phase, the analysis of Stage II will proceed in two part.

In the first **part**, an interim statistical report and interim summary document will be produced based on a database freeze initiated following collection of all immunogenicity **endpoints** and 28 days of both viral shedding and general safety follow-up following the last dose of **2018 candidates** administered to the last subject. This interim document will be unblinded to group, and will contain final summaries of **safety, immunogenicity and viral shedding** primary and secondary endpoints, although safety endpoints will be limited to the 28-day period after each vaccination only. This document will contain formal comparisons of these endpoints to corresponding endpoints collected in the historical control study, M2.

The second stage will be initiated following study completion for all subjects. The final statistical report and Clinical Study Report (CSR) will augment the interim reports with the additional safety follow-up and concomitant therapies collected in the extended follow-up phase. For example, tables of unsolicited adverse events which had originally been limited to the 28-day post-final-dose period will have a corresponding additional table to account for all events observed throughout the study period, including the extended safety follow-up.

### 10.1.3 *Initial Characteristics Data of the Subject Sample*

Descriptive statistics will be provided per group for demographic (e.g., age, weight, race, gender) and other initial subject characteristics (e.g., medical and surgical history, concomitant diseases).

Prior and concomitant medications will be coded using the WHO\_DRUG Dictionary.

### 10.1.4 *Immunogenicity Data*

For an overview of primary, secondary and exploratory endpoints, see Section 3.

#### *Neutralizing Type 2 Poliovirus Antibody Titers*

At each pre- and post-vaccination time point where neutralizing antibody titers are obtained:

- Seroconversion rates with 95% confidence intervals (CIs) will be computed.
- Seroconversion rates with 95% confidence intervals (CIs) will be computed from Day 0 at post-nOPV2 vaccination time points.
- Seroconversion rates with 95% confidence intervals (CIs) will be computed from Day -84 for infant groups.

- Median of log2 and geometric mean antibody titers will be computed along with 95% CIs.
- Plots of the reverse cumulative distribution of antibody titers will be generated.

### ***Viral Shedding***

Summaries of the detection of candidate vaccine via quantitative PCR and viral titer (log10 CCID50/g of stool) among those positive for virus will be computed by group and time point, for a subset of stool samples. A viral shedding index endpoint (SIE) will be calculated as the average of log10-transformed values of viral concentration in stool samples as determined using quantitative PCR (viral identity) and CCID50 (titer) from selected stool samples taken following each vaccine dose, and this index will be summarized by group.

Descriptive analysis and plots of the reverse cumulative distribution of the viral shedding index will be generated.

